8.2.3. Randomization

Once consent has been signed by the participant and study staff and the baseline assessment is complete, the staff member will randomize the participant. The randomization scheme is posted on the “SMART: Project 3 Regulatory” OneDrive file. Only appropriate staff have editing privileges for this document to avoid tampering. Participants will be immediately informed regarding the treatment arm they have been assigned to.

Participants will also be randomized to a counselor who will work with them throughout their participation in the study.

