3.6. Cascade of Events

3.6.1. Baseline Visit

1. Explain study to participants to see if they are interested in participating
2. Obtain informed consent
3. Screening for inclusion/exclusion criteria
4. Complete baseline assessment questionnaires (20 minutes)
5. Measures of buprenorphine-naloxone dose prescribed at this visit will be acquired from the medical record
6. Randomization

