10. ALTERNATIVE PROCEDURES: COVID

In the case that study staff are unable to recruit and provide the intervention in-person, the following alternative procedures will take place.

All individuals entering the CAS must abide by the rule of wearing a face mask at all times.

Procedures

Recruitment

Study staff will review the clinic schedule the day before and the day of to determine which patients are eligible. Study staff will come into the clinic to discuss the study and recruit eligible patients.

Enrollment

Consent

If the patient agrees to participate, the study staff will consent in person. The study team will take all precautions to protect themselves and the patient (e.g., PPE and practice social distancing).

For participants unable to complete consent in person and who have access to a computer, a DocuSign link will be sent immediately to conduct consent during the call. A blank copy of the consent form will be mailed to the participant

All other consent procedures will be the same as written above.

Randomization

Once the patient consents and completes baseline assessments, randomization procedures will stay the same as written above.

Baseline Assessment

Baseline assessment will take place in-person or over the telephone. Assessment must be completed prior to the participant's first physician return visit. Procedure will stay the same as written above.

Sessions 1-4

Following the Baseline Visit (BV), participants will complete sessions on the same schedule as their appointments at CAS, but windows will not exceed 30-day increments. Sessions and follow-up procedures will stay the same as written above with a few modifications (see below).

CM Session

Study staff will contact participants by phone or text to schedule a time to complete their assessment and CM intervention via Zoom call on the day of the participants' scheduled appointment. The participant will be given a 30-day window (starting with the day of their office visit) to complete the assessment or it must be completed prior to the next scheduled clinic visit for the patient.

If participant attends the physician appointment **and** has buprenorphine in urine:

Once the assessment is complete, the study staff will spin the number wheel while the participant is on the phone ("virtual wheel"). The study staff will inform the participant of the gift card amount earned and will immediately mail the gift card.

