14. VIRTUAL MAILING PROCEDURES

Session /Mailing Procedures:

Baseline

- If participant completes the full package in-person, they will receive a \$50 gift card before they leave the clinic.
 - Each interventionist is responsible for taking care of their own gift cards and welcome package (T-shirt, copy of consent, SOBER handout [BSM group only], and business card).

Instructions:

- Log gift cards out of the safe.
- Complete the GC sheet and make copy of gift card for study records.
 - Ppt. will need to sign off on the sheet. Once completed place in GC binder.
- Present GC to ppt
- Welcome ppt. to the study and hand them their welcome bag.
- Schedule next session (based on their appt. with clinic).

- If the participant takes the packet home, they will need to return the package back or call to complete the assessment over the phone. Once completed, we will mail them a \$50 gift card; if they come back into the clinic, we will give them a gift card in person.
 - Each interventionist is responsible for taking care of their own gift cards and welcome package (T-shirt, copy of consent, SOBER handout [BSM group only], and business card).

Instructions:

- Schedule a time to complete baseline.
 - Inform the ppt. that we will not be able to mail GC without completing the pack first.
- Welcome ppt. to the study and hand them their welcome bag.
 - T-shirt, copy of consent, SOBER handout [BSM group only], and contact card.
 - No GC will be given until pack is completed.

Once baseline is completed:

- Log gift cards out of the safe.
- Complete the GC sheet and make copy of gift card for study records.
 - Once completed place sheet in GC binder (ppt. will not need to sign).
- Mail GC to ppt.

- Mail can be dropped off at the UCH lobby or nearest postal office.
- Use SMART mailer and envelop.

Sessions 1-3 (Virtual)

- After the participant completes all the assessments and the intervention, they will receive their GC. Appointments will be scheduled within 30 day windows.

- **CM Group Instructions:**

- Complete assessments
- Inform ppt. of the GC amount they will receive, and to please allow 2-3 business days to arrive.
 - \$50 for completing assessments.
 - Additional GC will depend on the following:

Urine toxicology results

- If participant is compliant, buprenorphine in their urine, we will spin the virtual wheel for them and inform them of the amount received.

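### The take-home baseline route hands over an arm-dependent welcome bag before randomisation is allowed; view access to the allocation list and the limits of the Session 4 blind also need stating

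*Protocol*

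**What the plan says.** **Order of baseline and allocation.** Protocol Section 8.2.3 states that once consent is signed and "the baseline assessment is complete, the staff member will randomize the participant". Section 10 keeps that order under the COVID procedures: "Once the patient consents and completes baseline assessments, randomization procedures will stay the same as written above". Section 8.2.2 lets baseline be finished after the day of enrolment, provided it is done before Visit 1.

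Section 14 describes how a deferred baseline is handled: "If the participant takes the packet home, they will need to return the package back or call to complete the assessment over the phone". On that route staff book a time for baseline and hand over the welcome bag, listed as "T-shirt, copy of consent, SOBER handout [BSM group only], and contact card". The gift card is held back ("No GC will be given until pack is completed"); the bag is not. The steps for a finished baseline come afterwards.

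**Allocation list.** Section 8.2.3 places the scheme in a study OneDrive file and has a staff member randomise from it. The only access rule is "Only appropriate staff have editing privileges for this document to avoid tampering". Section 3.5.1 gives 1:1 allocation in fixed blocks of four. Section 4.3.4 has the interventionists recruit, consent and deliver both arms.

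**Session 4 assessor.** Sections 3.4.3 and 3.6.3 require the Part 2 assessor, a Research Assistant, to be blind. Section 4.3.5 also gives that assistant recruiting and consenting duties, and Section 8.8.1 gives post-session checks of forms and questionnaires. Section 14 has the assistant enter Session 4 amounts in the gift-card sheet that holds Session 1–3 amounts by participant ID.

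**The concern.** The take-home instruction can be carried out in full only if someone knows the arm before Section 8.2.3 lets it exist. A BSM participant could then complete baseline at home with BSM material in hand. Table 1 (Section 12.1) places delay discounting and the opioid purchase task at baseline. The SAP enters baseline values into its ANOVA and expects BSM to differ on discounting and opioid demand. A baseline shifted in one arm only feeds into the time-by-intervention effect.

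The other two points concern safeguards that are not written down. Protection against tampering is not concealment: staff who can foresee the next arm can influence whom they enrol and when, and that could affect every outcome. A blind assessor who works in records that separate the arms is blind only by self-restraint. Satisfaction, a primary outcome under Section 3.3, is collected on that call, as are follow-up delay discounting and substance-free activities.

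The trial is a pilot, but Section 3.2 makes its results the gateway to Project 4, and its procedures may be carried forward.

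**Working it through.** **1. Order conflict: the passages side by side**

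- Section 8.2.3: consent, baseline complete, randomise, tell the participant the arm.
- Section 14, take-home route: book baseline, hand over the bag (BSM handout for one arm), baseline completed later, gift card sent.
- When the bag changes hands on the second route, the first says no arm has been assigned.
- In-person route in Section 14: the full package is completed before the participant leaves, and Section 3.6.1 puts randomisation last in the baseline visit. No conflict.
- Section 8.5.2, the Session 1 preparation list and the handout page in Section 13 all place the handout at baseline. They agree with Section 8.2.3 when baseline is done in one visit and conflict only when it is deferred.

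The number of deferred baselines is not given. Assuming 10%, 25% or 50%: 0.10 × 40 = 4, 0.25 × 40 = 10, 0.50 × 40 = 20 participants. With 1:1 allocation about half (2, 5 or 10) would be in BSM and hold the handout.

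**2. Allocation list**

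The plan's own figure first: 40/4 = 10 blocks, 10 × 2 = 20 per arm, as stated in Section 3.5.

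- If enrolling staff can view the list: 40 of 40 assignments are knowable.
- If they cannot, but know all past assignments and block starts and enrolment is strictly sequential, enumerate the 6 orderings of a block:
  - Chance that the next arm is certain, places 1 to 4: 0, 0, 1/3, 1. Mean = (4/3)/4 = 1/3, or 13.3 of 40.
  - Best-guess accuracy, places 1 to 4: 1/2, 2/3, 2/3, 1. Mean = 17/24 = 70.8%, or 28.3 of 40, against 20 by chance.
  - These are upper ends; deferred baselines disturb the order and lower them.
- Restricting view access changes only the first case. The block size stays the same, and interventionists who deliver both arms still learn past assignments. The 1/3 and 70.8% are therefore not the benefit of the fix.

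**3. Gift-card sheet**

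Inputs: \$50 per assessment (Section 8.8.2); wheel values \$25, \$50 and \$100 (Section 8.5.1).

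- CM session with a spin: 50 + 25 = 75, 50 + 50 = 100, 50 + 100 = 150.
- CM session without a spin: 50.
- BSM session: 50 (or 25, the figure in the Section 13 scripts, if that were logged).

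If amounts are logged as session totals, any row above 50 identifies CM; a row of 50 does not separate the arms. Adherence rates are not given. Assuming 30%, 50% or 70% per visit, CM participants with at least one such row over Sessions 1–3 are:

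- Independent visits, 20 × [1 − (1 − p)³]: 20 × 0.657 = 13.1; 20 × 0.875 = 17.5; 20 × 0.973 = 19.5.
- The same people adherent every time, 20 × p: 6, 10 or 14.

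These count participants whose rows could show the arm, not calls on which the assessor knew it.

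**The case against.** **Order conflict.** Nobody belongs to the BSM group before randomisation, so staff who respect Section 8.2.3 could simply leave the handout out of the bag. The same contents list appears on the in-person route, so it may be carried-over wording. That is a sensible workaround, but it departs from the Section 14 list, and the Session 1 preparation in Section 13 still expects the handout to have been received at baseline. A reader might go further and infer that participants are told their arm before baseline. The documents do not support that: the handout is a breathing exercise that names no arm, and nothing says participants know the bags differ. It could hint at the arm, no more. The link to substance-free activities is also looser than it looks: the SAP speaks of time allocated, whereas the repeated measure in Section 12.2.16 rates helpfulness. Delay discounting is the cleaner example.

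**Allocation list.** This rests on silence. Editing is controlled, staff are trained in randomisation (Section 5.1), and on the standard route physicians raise the study and confirm the visit schedule (Sections 6 to 8.1). Enrolment is therefore not in staff hands alone, although research staff check eligibility and consent, and under Section 10 "Study staff will review the clinic schedule the day before and the day of to determine which patients are eligible". That recruiters have seen the list is not shown.

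**Assessor.** The assistant enters a participant's Session 4 amount after Part 2 is complete, so earlier exposure would come from opening the sheet for others. Nothing says earlier rows are consulted. A reader might infer that the database checks expose CM wheel photos, but Section 8.8.1 covers paper forms and questionnaires only. Participants know their arm, and the open-ended satisfaction items on effective components, improvements and motivation (Section 12.2.21) can reveal it. No reallocation of tasks cures that.

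**Conclusion.** The order conflict is an error in the text, confined to deferred baselines. How many participants it touches is unknown; 4 to 20 of 40 rests wholly on an assumed 10% to 50% deferral, and the size of any shift in baseline answers cannot be derived from the documents.

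The other two parts are inexpensive improvements, not demonstrated faults. Foreknowledge is possible for all 40 assignments if the list can be viewed; whether it can is not stated. The gift-card sheet can show the arm for many CM participants at plausible adherence, on the assumption that winnings are entered in the session total; actual unblinding is not shown.

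Adherence, judged from attendance and urine results, is not exposed to the handout or to the assessor's knowledge. It would be exposed, like any outcome, to selective enrolment if the list were foreseen.

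**What to change.** 1. Reconcile Section 14 with Sections 8.2.3 and 10: no arm-specific material is given until baseline is complete and the participant is randomised. Add the same wording, for deferred baselines, to Section 8.5.2 and to the Session 1 preparation and handout page in Section 13. The Session 1 script already gives or sends the handout, so no content is lost and the cost is wording only.

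2. Limit viewing of the scheme to existing staff who do not enrol, for example the manager who maintains the database (Section 4.3.2). Release one assignment at a time after consent and baseline are complete. The cost is file permissions and a release step. Because participants are told their arm at once, the holder or a locked release must be available at randomisation. This does not remove the predictability of fixed blocks of four and should not be presented as doing so.

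3. For participants the assistant will assess, have interventionists do the gift-card logging and post-session checks, using the completion notice the assistant already sends, and do not let the assistant randomise them. Some tasks shift; no staff are added. Describe the blind as limited, since participants know their arm and the satisfaction items can disclose it.

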8.4. Tasks to Complete Prior to the Session

Please remember: Both CM and BSM conditions need to be recorded.

8.5 Session Windows

Following the Baseline Visit, participants will complete 4 sessions in no greater than 30-day increments. These visits will be referred to as Session 1 (S1), Session 2 (S2), Session 3 (S3), Session 4 (S4). The window scheduling guidelines for sessions are as follow:

- S1 opens when their 1st physician return visit is scheduled.
- S1 closes the day before their S2 is scheduled OR at 30 days from S1 window open.
- S2 opens when their 2nd physician return visit is scheduled or the day after S1 window closes (e.g. if S1 is not completed in order to keep under the 30 day maximum).
- S2 closes the day before their S3 is scheduled OR at 30 days from S2 window open.
- S3 opens when their 3rd physician return visit is scheduled or the day after S2 window closes.
- S3 closes the day before their S4 is scheduled OR at 30 days from S3 window open.
- S4 opens when their 4th physician return visit is scheduled or the day after S3 window closes.
- S4 closes 4 weeks from S4 window open (but continue to try to assess).

8.6. Intervention Sessions

Prior to the session, Interventionists will prepare for the brief assessment conducted during each treatment session by finding the participant in the Filemaker database, or if offline, entering the participant information on the top of the assessment materials.

Interventionists will also prepare to administer the appropriate session (1, 2, 3, or 4) (within the appropriate condition).

In addition, Interventionists will prepare the recording device to ensure that the session is recorded. If remote, the interventionist will text or email the participant a Zoom telephone number with a meeting ID for them to call and be placed in a meeting. The interventionist will ensure that Zoom is recording once permission is granted from participant. All sessions will be recorded and uploaded to OneDrive folder (SMART Project 3/Recordings) and labeled with the participant's study ID, session number (1, 2, 3, 4), condition (CM vs. BSM), and staff initials. (e.g. 301 S2 BSM AB)

At each session , the Interventionist will meet with the participant to complete the assessment questionnaires and complete the intervention – either a BSM session or a wheel spin for additional gift cards for CM (if requirements are met).

If the participant drops out of treatment at the Center for Addiction Science, they will no longer receive the CM or BSM. However, all assessments will be conducted regardless of the participant's adherence to medical treatment at the CAS. Upon completion of the assessment, participants will still earn the \$50 gift card. This will allow us to understand the reason for the participant's non-adherence to treatment, and to evaluate whether these individuals pursue treatment elsewhere.

The intervention scripts are available in section 13 of the manual of procedures.

8.5.1 CM Intervention Description

Record all interactions with CM participants.

Participants who are assigned to CM will complete their assessments with the Interventionist. After the assessments are complete, the study staff will check the results of the urine screen. In the event that a participant misses their clinic visit, assessments may still be completed at any time during the window. If the participant completes their clinic visit **before the session window closes** they may be contacted to complete a wheel spin, if eligible.

Adherent (buprenorphine present in urine)

If the participant is determined as adherent (i.e., buprenorphine present in urine), they will spin a computer number wheel with varying value gift card amounts (\$25-\$100) with a bonus \$100 gift card given for consecutive adherence (attendance at the clinic and buprenorphine present in urine) across all 4 sessions . The number wheel will consist of 4 \$25 gift cards, 3 \$50 gift cards, and 3 \$100 gift cards.

Non-Adherent (buprenorphine not present in urine)

If the participant is determined as non-adherent (i.e., buprenorphine not present in urine), they will NOT spin the number wheel.

8.5.2. BSM Intervention Description

Record all interactions with BSM participants.

Participants who are assigned to BSM will complete their assessments with the interventionist. After the assessments are complete, the interventionist will engage the participant in the BSM intervention. A SOBER handout will be given to the participant at their baseline visit (*See section 13*). Participants will also receive a Tips for Improving Self-Control handout at session 4.

If a participant misses a session, the interventionist will continue with the next session in numerical order. So, if a participant is on S2 and missed S1, the interventionist will deliver S1 content during session 2.

This intervention consists of 4 sessions:

Session 1

This session will cover reasons for attending treatment, goals, time spent on valued activities, future events, and mindfulness-based coping (SOBER).

Session 2

This session will substance goals check in, substance free activities, and mindfulness-based coping (SOBER).

Session 3

This session will cover goals check in, substance free activities check in, and mindfulness-based coping (SOBER).

Session 4

This session will cover self-control improvement, and review goals, substance free activities, and mindfulness-based coping (SOBER).

In the event that a participant misses their clinic visit, assessments may still be completed at any time during the window. If the participant completes their clinic visit **before the session window closes** they may be contacted to complete a counseling session.

8.6. Distressed Participant Procedures

Detecting severe emotional distress is the responsibility of all SMART staff who interact with participants.

8.6.1. Warning Signs

Warning signs include:

- Talking about/making plans for suicide (“I’m going to end it.”)
- Expressing hopelessness about the future (e.g., Things will never get better for me...”)
- Displaying severe/overwhelming emotional pain or distress (“I can’t take this anymore, I’m at a breaking point!”)
- Showing worrisome behavioral cues or marked changes in behavior, particularly in the presence of the warning signs above. Specifically, this includes significant withdrawal from social connections/situations, changes in sleep (increased or decreased), anger or hostility that seems out of character or out of context, recent increased agitation or irritability

People may give direct as well as indirect verbal cues about suicidal thoughts. These typically communicate feelings of being trapped, helpless, and hopeless

SMART staff should use clinical judgment to further assess whether distress indicates lasting and unchanging conditions:

Example of limited distress (time-limited/likely to change):

- Participant: “My husband is driving me crazy! I can’t take this anymore!”
- Interventionist: “Sounds like you’re experiencing some stress right now.”
- Participant: “Yeah, but he’s only doing overtime this week. Next week we’re back to normal.”
- Example of lasting/unchanging distress:
- Participant: “I lost another job, the third one in a row. It never gets better.”
- Interventionist: “Sounds like you’re experiencing some stress right now.”
- Participant: “Yeah, I’m useless, always have been. I’m a burden to my family. At least if I died they could get the insurance money.”

8.6.2. Clinic Distress Procedure

If the participant is seen in the clinic, the interventionist will follow UCH’s Behavioral Health Emergency-Suicidal Ideation procedure (policy number: BH.001), which requires that the study staff inform the behavioral specialist on staff or clinic doctor ([name]).

8.6.3. Telephone/Zoom Distress Procedure

During phone assessments and psychosocial intervention sessions, the interventionist will follow the procedures below. If the participant is not at the clinic, the following rules will be enacted:

1. Initiate Discussion:
 - a. *"I am concerned about you. It sounds like you are experiencing very serious emotional distress right now. Before we continue with the session, I am going to need to ask you some questions to ensure you are doing ok."*
2. Get physical location
 - a. *"Just in case we get disconnected, I am going to need you to tell me where you are. Sometimes, when people feel this upset, they need immediate help, and I want to make sure I can provide that for you."*
3. Assess for suicidal ideation/intent/plan:

“Let me ask you some questions about how severe your distress is.”

Suicide Behaviors Questionnaire-Revised (fillable for printout)

Osman eta/ (1999) Revised. Permission for use granted by A. Osman, MD

Question	Possible answers	Points	Subtotal
1. Have you ever thought about or attempted to kill yourself?	Never It was just a brief passing thought I have had a plan at least once to kill myself but did not try to do it I have had a plan at least once to kill myself and really wanted to die I have attempted to kill myself, but did not want to die I have attempted to kill myself, and really hoped to die	1 2 3 3 4 4	
2. How often have you thought about killing yourself in the past year?	Never Rarely (1 time) Sometimes (2 times) Often (3-4 times) Very Often (5 or more times)	1 2 3 4 5	
3. Have you ever told someone that you were going to commit suicide, or that you might do it?	No Yes, at one time, but did not really want to die Yes, at one time, and really wanted to die Yes, more than once, but did not want to do it Yes, more than once, and really wanted to do it	1 2 2 3 3	
4. How likely is it that you will attempt suicide someday?	Never No chance at all Rather unlikely	0 1 2	

	Unlikely	3	
	Likely	4	
	Rather likely	5	
	Very likely	6	
TOTAL FOR ALL ITEMS:			

Scoring:

< 4 = Not reportable	Assessment will be documented. "It sounds like you are definitely experiencing some distress, but you have a handle on it at the moment."
	Provide list of resources.
	Document events in file.
4-6 = Mild to Moderate Distress	Assessment will be documented.
	Participant will be provided a listing of community resources and encouraged to seek help. "It sounds like you are definitely experiencing some distress. I encourage you to consider reaching out to one of these organizations for help or support."
	Provide list of resources.
	Document events in file.
7 or more points but no immediate plan = Severe Distress and Suicidal Ideations, With No Intent or Plan	Develop an action plan to get help from a mental health professional. The action plan will be documented. "You are definitely experiencing distress but it sounds like you are not in immediate danger of self-harm. Is this correct?" "I would like to come up with a plan to help you get some support. Is there someone you can talk to about your distress?"
	Provide list of resources.
	Document events in file.
	Follow up with participant in two days to ensure help seeking is occurring.
	Document follow up in file.
	Severe distress incidents will be reported to an on-site Clinical Supervisor ([name]).
7 or more points and immediate plan = Severe Distress and Suicidal Ideations With Intent or Plan	Maintain contact with the participant and put the patient in touch directly with emergency services (either by phone if in person or by calling 911, if on telephone). Maintain contact until responsibility is transferred.

	“Because you indicated to me that you intend to harm yourself and that this is likely, I am going to remain with you (on the phone) until help arrives. I am going to call emergency services to come speak with you at the address you provided me at the start of these questions. While I arrange this, I want to keep speaking with you about how you are feeling and what you need to do to feel better.”
	If crisis situation (i.e., person is very agitated), may need to text another staff member to call local 911 and provide address This works even if the person is not in Memphis – the police will transfer the information to the local precinct.
	
 ▪ National Suicide Prevention Lifeline: 1 [contact] 
 ○ Hours: 24 hours, 7 days a week ○ Languages: English, Spanish ○ Website: www.suicidepreventionlifeline.org)
	Contact [name] to alert her to the situation, during or immediately after.
	All actions should be documented in file.
	Severe distress incidents will be reported to an on-site Clinical Supervisor ([name]).

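### In the remote distress procedure, the choice between a two-day follow-up and emergency services turns on an immediate plan that no printed item asks about

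*Protocol*

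**What the plan says.** Section 8.6.3 applies when the participant is not at the clinic. Staff open the discussion, obtain the participant's location, and then reach Step 3, headed "Assess for suicidal ideation/intent/plan". Four scored items follow:

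- Item 1 covers lifetime thoughts or attempts. It is the only item that mentions a plan, and it does so as history, for example "I have had a plan at least once to kill myself but did not try to do it".
- Item 2 covers how often the participant thought of suicide in the past year.
- Item 3 covers ever having told someone.
- Item 4 asks "How likely is it that you will attempt suicide someday".

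The scoring table has two rows at the top of the range:

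- "7 or more points but no immediate plan = Severe Distress and Suicidal Ideations, With No Intent or Plan" leads to a documented action plan toward professional help, a resource list and contact again after two days. Its script includes "it sounds like you are not in immediate danger of self-harm. Is this correct".
- "7 or more points and immediate plan = Severe Distress and Suicidal Ideations With Intent or Plan" leads to continuous contact until emergency services take over. Its script begins "Because you indicated to me that you intend to harm yourself and that this is likely".

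Both rows require a report to a clinical supervisor. In-clinic contacts follow a separate policy (section 8.6.2) and are outside this point.

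**The concern.** The most consequential branch in the procedure depends on a fact that the printed items do not collect. Step 3 promises an assessment of intent and plan, but every item looks back over a lifetime or a year, or forward to an unspecified day.

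The one scripted check on present danger does not fill the gap. It sits in the no-plan row, so it is reached only after the participant has provisionally been placed there. It offers the reassuring answer and asks for agreement, and no step is printed for a participant who disagrees. The emergency script, in turn, speaks as though intent has already been stated.

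At stake is a remote participant who has a current plan but does not volunteer it. Staff who follow the page could give that person an action plan and a call two days later instead of emergency help. Section 3.1 asks staff to keep closely to the manual, so the printed wording matters.

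**Working it through.** The plan gives no figure to reproduce. The check is whether the total, or the answers behind it, can separate the two severe rows.

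**Inputs (section 8.6.3).** Points by answer option: item 1 {1, 2, 3, 3, 4, 4}; item 2 {1, 2, 3, 4, 5}; item 3 {1, 2, 2, 3, 3}; item 4 {0, 1, 2, 3, 4, 5, 6}.

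**All answer patterns.** 6 × 5 × 5 × 7 = 1,050. Totals run from 1 + 1 + 1 + 0 = 3 to 4 + 5 + 3 + 6 = 18.

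| Total | Patterns |
|---|---|
| Below 4 | 1 |
| 4 to 6 | 53 |
| 7 or more | 996 |

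**Patterns at 7 or more that rule out a current plan at face value.**
- Item 1 at 1 or 2 points (no plan or attempt ever): 147 + 161 = 308.
- Item 1 at 3 or 4 points, but item 2 at 1 point (no thought in the past year): 130.
- Together: 308 + 130 = 438.

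**Patterns that fit either severe row.** 996 − 438 = 558, and 558/996 = 56%. Cross-check: item 1 at 3 or 4 with item 2 at 2 or more gives 4 × 4 × 5 × 7 = 560 patterns, of which 2 total below 7, leaving 558.

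**Sensitivity to how item 4 is read.**
- If the two lowest answers (0 and 1 points) are also taken to rule out intent: 4 × 4 × 5 × 5 = 400, all totalling at least 3 + 2 + 1 + 2 = 8; 400/996 = 40%.
- If every answer up to and including Unlikely (3 points) is taken that way: 4 × 4 × 5 × 3 = 240; 240/996 = 24%.

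**Can the total act as a proxy?** No. History alone can reach the severe range: a past attempt (4), no thought in the past year (1), having told someone more than once (3) and the lowest answer on item 4 (0) give 4 + 1 + 3 + 0 = 8. A past plan (3), some thoughts in the past year (3), never having told anyone (1) and a likely future attempt (4) give 3 + 3 + 1 + 4 = 11, and these answers are the same whether or not the person has a plan today.

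**Below 7.** A current plan answered consistently scores at least 3 + 2 + 1 + 1 = 7. The only two exceptions among the 560 patterns both total 3 + 2 + 1 + 0 = 6, so a gap below 7 requires inconsistent or concealed answers.

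**The case against.** The strongest reply is that staff are already told to establish the plan. Step 3 names intent and plan, and a row conditioned on an immediate plan obliges them to find out. Talk of suicide plans is the first warning sign in section 8.6.1, which adds "SMART staff should use clinical judgment to further assess whether distress indicates lasting and unchanging conditions". Item 4 comes close to intent, and the emergency script seems to echo it. A participant who answers no to the prompt in the no-plan row no longer meets that row's condition, and the next row is the emergency one. Location is obtained first, interventionists have weekly supervision (section 4.3.4), and the BSM script carries a mandated-reporter statement. The pattern counts carry no frequencies and move with the reading of item 4.

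Much of this stands as mitigation. The gap is a missing question, not a missing instruction, and a plan that is voiced would probably be caught. The counts show only that the answers cannot separate the rows.

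The gap itself remains. Item 4 asks about someday and is not named as the deciding rule. The passage on clinical judgment concerns whether distress is lasting. Supervision and reporting do not supply the answer before a row is chosen. The mandated-reporter statement is not a question, and the CM script lacks it although section 10 allows CM sessions by Zoom.

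**Conclusion.** The concern holds for remote contacts. The printed items do not elicit a current plan or intent, yet that alone separates the two rows at 7 or more points. Between 24% and 56% of the answer patterns in that range fit either row, depending on how item 4 is read. These are unweighted patterns and say nothing about how often the situation will arise among about 40 participants. The gap below 7 is narrow (2 of 560 patterns) and secondary.

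Two limits apply. Material directly after the scoring table was not available for this review, so the finding covers the printed items and rows only. Calling the prompt leading is a judgement, though its wording does supply the answer it seeks. No statistical result is affected. The change should be made because the possible harm is irreversible and the remedy is cheap.

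**What to change.** In Step 3, after item 4 and before any row is chosen, add one scripted question asked of everyone, for example: *Right now, do you have a plan or an intention to kill yourself?* The clinical supervisors should confirm the wording. Asking about both plan and intention matches the label of the emergency row, and the opening words keep the question on the present.

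Add one sentence: a current plan or intent confirmed by that question leads to the emergency row even if the total is below 7. A warning-sign remark made earlier is followed up with the same question and does not by itself trigger the emergency row, so the clinical judgment in section 8.6.1 is kept.

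The cost is one question and one sentence on one procedure page, with no extra staff. The downside is a slightly longer distress call and an occasional additional emergency referral. Because the sentence opens the emergency row to some totals below 7, the supervisors should approve it as a triage decision.
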